10.2.2.5. B-cell ELISPOT assay

B-cell ELISPOT will be used to quantify vaccine antigen-specific memory B-cells which are responsible for long term (humoral) memory and will be the cells recalled during an infection subsequent to vaccination. This assay is designed to evaluate the frequency (per million memory B-cells) of HBs-specific memory B-cells from peripheral blood samples.

PBMCs are stimulated with Cytosine phosphate Guanine (CpG) for 5 days to induce *in vitro* cell differentiation. Differentiated cells (plasmablasts) are then incubated with IgG antibody directed against immunoglobulins (to quantify total memory B-cells) or with the recombinant HBs protein (to quantify vaccine specific memory B-cells) coated on nitrocellulose plates. Antibodies bound to their target are revealed by the addition of a secondary antibody, an antibody/substrate complex allowing colorimetric detection. Finally, the plate(s) are read and analyzed on an ELISPOT reader. This B-cells ELISPOT is an optimized assay.

The clinical testing will be performed at GSK laboratory (Rixensart, Belgium).

CCI

CCI

10.3. Appendix 3: Adverse Events: definitions and procedures for recording, evaluating, follow-up, and reporting

10.3.1. Definition of an AE

An AE is any untoward medical occurrence (an unfavorable/unintended sign - including an abnormal laboratory finding), symptom, or disease (new or exacerbated) in a clinical study participant that is temporally associated with the study intervention. The AE may or may not be considered related to the study intervention.

10.3.1.1. Events Meeting the AE Definition

- Significant or unexpected worsening or exacerbation of the condition/indication under study.
- Exacerbation of a chronic or intermittent pre-existing condition including either an increase in frequency and/or intensity of the condition.

- New conditions detected or diagnosed after administration of the study intervention even though they may have been present before study start.
- Signs, symptoms, or the clinical sequelae of a suspected drug, disease or other interaction.
- Signs, symptoms, or the clinical sequelae of a suspected overdose of either the study intervention or a concurrent medication.
- Signs or symptoms temporally associated with administration of the study intervention.
- Signs, symptoms that require medical attention (e.g., hospital stays, physician visits and emergency room visits).
- Significant failure of an expected pharmacologic or biological action.
- Pre- or post- intervention events that occur as a result of protocol-mandated procedures (i.e., invasive procedures, modification of participant's previous therapeutic regimen).
- Clinically significant abnormal laboratory findings or other abnormal assessments that are present at baseline and significantly worsen following the start of the study will also be reported as AEs or SAEs.
- AEs to be recorded as solicited AEs are described in Section 10.3.3. All other AEs will be recorded as UNSOLICITED AEs.

10.3.1.2. Events NOT Meeting the AE Definition

- Situations where an untoward medical occurrence did not occur (e.g., social and/or convenience admission to a hospital, admission for routine examination).
- Anticipated day-to-day fluctuations of pre-existing disease(s) or condition(s) present or detected at the start of the study that do not worsen.
- Pre-existing conditions or signs and/or symptoms present in a participant before the first dose of study intervention. These events will be recorded in the medical history section of the eCRF.
- Hospitalization for elective treatment of a pre-existing condition (known or diagnosed before signing the informed consent) that did not worsen from baseline.
- Any clinically significant abnormal laboratory findings or other abnormal safety assessments associated with the underlying disease, unless judged by the investigator to be more severe than expected for the participant's condition.

10.3.2. Definition of an SAE

An SAE is any untoward medical occurrence that:	
a. Results in death.	
b. Is life-threatening.	
Note: The term ‘life-threatening’ in the definition of ‘serious’ refers to an event in which the participant was at risk of death at the time of the event. It does not refer to an event, which hypothetically might have caused death, had it been more severe.

c. Requires hospitalization or prolongation of existing hospitalization.	
Note: In general, hospitalization signifies that the participant has been admitted (usually involving at least an overnight stay) at the hospital or emergency ward for observation and/or treatment that would not have been appropriate in the physician’s office or outpatient setting. Complications that occur during hospitalization are AEs. If a complication prolongs hospitalization or fulfills any other serious criteria, the event is serious. When in doubt as to whether “hospitalization” occurred or was necessary, the AE should be considered serious.
 
Hospitalization for elective treatment of a pre-existing condition that did not worsen from baseline is not considered an AE.

d. Results in disability/incapacity.	
Note: The term disability means a substantial disruption of a person’s ability to conduct normal life functions.
 
This definition is not intended to include experiences of relatively minor medical significance such as uncomplicated headache, nausea, vomiting, diarrhea, influenza like illness, and accidental trauma (e.g., sprained ankle) which may interfere or prevent everyday life functions but do not constitute a substantial disruption.

e. Is a congenital anomaly/birth defect in the offspring of a study participant.	
f. Abnormal pregnancy outcomes (e.g., spontaneous abortion, fetal death, stillbirth, congenital anomalies, ectopic pregnancy).	
g. Other situations.	
Medical or scientific judgment must be exercised in deciding whether reporting is appropriate in other situations. Important medical events that may not be immediately life-threatening or result in death or hospitalization but may jeopardize the participant or require medical or surgical intervention to prevent one of the other outcomes listed in the above definition should be considered serious. Examples of such events are invasive or malignant cancers; intensive treatment in an emergency room or at home for allergic bronchospasm; blood dyscrasias; and convulsions that do not result in hospitalization.

10.3.3. **Solicited events**

Solicited events are predefined administration site events and systemic events for which the participant is specifically questioned, and which are noted by the participant in their eDiary.

a. **Solicited administration site events**

The following administration site events will be solicited:

Table 23 Solicited administration site events

Pain at administration site
Redness at administration site
Swelling at administration site

b. **Solicited systemic events**

The following systemic events will be solicited:

Table 24 Solicited systemic events

Fever
Fatigue
Myalgia
Arthralgia
Headache
Chills
Malaise
Loss of appetite
Nausea
Vomiting
Diarrhea

Note: participants will be instructed to measure and record the oral temperature in the evening. If additional temperature measurements are taken at other times of the day, participants will be instructed to record the highest temperature in the eDiary. Other options for temperature records include the axilla, ear canal and forehead; but oral temperature remains the preferred option.

10.3.4. **Unsolicited AEs**

An unsolicited AE is an AE that was either not included in the list of solicited events or could be included in the list of solicited events but with an onset outside the specified period of follow-up for solicited events. Unsolicited events must have been spontaneously communicated by a participant who has signed the informed consent. Unsolicited AEs include both serious and non-serious AEs.

Potential unsolicited AEs may be medically attended (i.e., symptoms or illnesses requiring a hospitalization, or an emergency room visit, or visit to/by a health care provider). The participants will be instructed to contact the site as soon as possible to report medically attended event(s), as well as any events that, though not medically attended, are of participant's concern. Detailed information about reported unsolicited AEs will be collected by qualified site personnel and documented in the participant's records.

Unsolicited AEs that are not medically attended or perceived as a concern by the participant will be collected during an interview with the participants and by review of available medical records at the next visit.

10.3.5. Adverse events of special interest (AESIs)

pIMDs are the only AESIs collected during this study.

10.3.5.1. Potential immune-mediated disorders

Potential immune-mediated disorders (pIMDs) include autoimmune diseases and other inflammatory and/or neurologic disorders of interest which may or may not have an autoimmune etiology. AEs that need to be recorded and reported as pIMDs include those listed in [Table 27](#) (refer to Section [10.3.8.1](#) for reporting details).

The investigator must exercise his/her medical/scientific judgment to determine whether other diseases have an autoimmune origin (i.e., pathophysiology involving systemic or organ-specific pathogenic autoantibodies) and should also be recorded as a pIMD.

In addition, the investigator should categorize each pIMD either as a new onset condition (if it started following vaccination) or as an exacerbation of a preexisting chronic condition (if it exacerbated following vaccination) in the eCRF.

When there is enough evidence to make any of the diagnoses mentioned in [Table 27](#), the AE must be reported as a pIMD. Symptoms, signs or conditions which might (or might not) represent the above diagnoses, should be recorded and reported as AEs but not as pIMDs until the final or definitive diagnosis has been determined, and alternative diagnoses have been eliminated or shown to be less likely.

In order to facilitate the documentation of pIMDs in the eCRF, a pIMD standard questionnaire and a list of preferred terms (PTs) will be available to investigators at study start.

Once a pIMD is diagnosed (serious or non-serious) in a study participant, the investigator (or designate) must complete, date and sign an electronic Expedited Adverse Events Report.

The list of pIMDs is provided in Section [10.9](#) (Appendix 9).

10.3.6. Clinical laboratory parameters and other abnormal assessments qualifying as AEs or SAEs

In the absence of a diagnosis, abnormal laboratory findings assessments (hematology or clinical chemistry) or other abnormal results the investigator considers clinically significant will be recorded as an AE or SAE, if they meet the definition of an AE or SAE (refer to Sections 10.3.1 and 10.3.2).

The investigator must exercise his or her medical and scientific judgment in deciding whether an abnormal laboratory finding, or other abnormal assessment is clinically significant.

10.3.7. Events or outcomes not qualifying as AEs or SAEs**10.3.7.1. Pregnancy**

Female participants who become pregnant after the first study intervention dose must not receive subsequent doses of the study intervention but may continue other study procedures at the discretion of the investigator.

While pregnancy itself is not considered an AE or SAE, any abnormal pregnancy outcome or complication or elective termination of a pregnancy for medical reasons will be recorded and reported as an SAE. Please refer to Section 10.3.2 for definition of SAE.

Note: The pregnancy itself should always be recorded on an electronic pregnancy report. The following should always be considered as SAE and will be reported as described in Section 10.3.8 and Section 10.3.10:

- Spontaneous pregnancy loss, including:
 - Spontaneous abortion, (spontaneous pregnancy loss before/at 22 weeks of gestation).
 - Ectopic and molar pregnancy.
 - Stillbirth (intrauterine death of fetus after 22 weeks of gestation).
- Note: the 22 weeks cut-off in gestational age is based on WHO-International Classification of Diseases 10 noted in the EMA Guideline on pregnancy exposure [EMA, 2006]. It is recognized that national regulations might be different.
- Any early neonatal death (that is death of a live born infant occurring within the first 7 days of life).
- Any congenital anomaly or birth defect (as per [CDC] guidelines) identified in the offspring of a study participant (either during pregnancy, at birth or later) regardless of whether the fetus is delivered dead or alive. This includes anomalies identified by prenatal ultrasound, amniocentesis or examination of the products of conception after elective or spontaneous abortion.

Furthermore, any SAE occurring as a result of a post-study pregnancy AND considered by the investigator to be reasonably related to the study vaccine will be reported to GSK Global Safety as described in Section 10.3.10. While the investigator is not obligated to actively seek this information from former study participants, he/she may learn of a pregnancy through spontaneous reporting.

10.3.8. Recording and follow-up of AEs, SAEs, pIMDs and pregnancies

The participants will be instructed to contact the investigator immediately should they experience any signs or symptoms they perceive as serious.

When an AE/SAE occurs, it is the investigator's responsibility to review all documentation (e.g., hospital progress notes, laboratory and diagnostics reports) related to the event. The investigator will then record all relevant information regarding an AE/SAE on the eCRF. The investigator may not send photocopies of the participant's medical records to GSK instead of appropriately completing the eCRF.

There may be instances when copies of medical records for certain cases are requested by GSK. In this case, all participant identifiers will be blinded on copies of the medical records prior to submission to GSK.

The investigator will attempt to establish a diagnosis pertaining to the event, based on signs, symptoms, and/or other clinical information. In such cases, the diagnosis should be documented as the AE/SAE instead of individual signs/symptoms.

Electronic Diary (eDiary) will be used in this study to capture solicited administration site or systemic events. The participant should be trained on how and when to complete the eDiary.

Participants should be trained on using the eDiary. This training must be documented in the participant's source record.

Verify completed eDiary (via the web portal) during discussions with the participant at subsequent contacts (visit or phone call) after Dose 1 and Dose 2 of the study intervention administration.

Any unreturned eDiary will be sought from the participant through telephone call(s) or any other convenient procedure.

Refer to the SPM for more information regarding the use of eDiary.

10.3.8.1. Time period for collecting and recording AEs, SAEs, MAEs, pIMDs and pregnancies

All solicited events that occur up to 14 days following administration of Dose 1 and Dose 2 of study intervention (Day 1 to Day 14 and Day 31 to Day 44, respectively) must be recorded into the eDiary, irrespective of intensity. All other AEs occurring within 31 days following Dose 1 and Dose 2 of study intervention administration should be recorded onto the appropriate section of the eCRF, irrespective of their intensity or whether or not they are considered related to the study intervention.

The time period for collecting and recording of SAEs, MAEs, pIMDs, and pregnancies will begin at the first receipt of study interventions and will continue throughout the whole study period.

All AEs/SAEs leading to withdrawal from the study will be collected and recorded from the time of the first receipt of study intervention until the participant is discharged from the study. SAEs related to study participation or to a concurrent GSK medication/vaccine will be collected from the time consent is obtained until the participant is discharged from the study.

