Visit 7 → Visit 9 ⁴	300 days (10 months)	286-314 days
Visit 8 → Visit 9 ³	180 days (6 months)	166-194 days

PC = phone contact

¹Whenever possible the investigator should arrange study visits within this interval.

²Participants will not be eligible for inclusion in the Per-Protocol Set for analysis of immunogenicity if they make the study visit outside this interval.

³For participants in the HBs-alum group.

⁴For participants in all groups except the HBs-alum group.

CCI

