3. OBJECTIVES AND ENDPOINTS

Table 3 Study objectives and endpoints

Objectives	Endpoints	Primary
To evaluate the reactogenicity and safety in all study groups.	
 Percentage of participants with solicited administration site and systemic AEs within 14 days (Day 1 till Day 14) after Dose 1 and Dose 2. Duration of solicited AEs (administration site and systemic) after Dose 1 and Dose 2. Percentage of participants with any unsolicited AEs within 31 days (Day 1 till Day 31) after Dose 1 and Dose 2. Percentage of participants with SAEs, MAEs and AEs leading to study withdrawal throughout the entire study period. Percentage of participants with pIMDs throughout the entire study period. The absolute values and changes in hematology and biochemistry parameters post-Dose 1 (Day 8 and Day 31) and post-Dose 2 (Day 38 and Day 61) from baseline (pre-vaccination, Day 1). 	

CONFIDENTIAL

215301 (EARLY-CLINRES-017)

Protocol Amendment 4 Final

Objectives	Endpoints
	
 Percentage of participants with abnormal laboratory parameter values at pre-vaccination (Day 1), post-Dose 1 (Day 8 and Day 31) and post-Dose 2 (Day 38 and Day 61).
	Secondary
To evaluate the humoral immune response in all study groups.	
 GMC of Anti-HBs Ab concentrations at Day 1, Day 31, Day 61 and Day 361. Anti-HBs seroconversion and seroprotection rates at Day 31, Day 61 and Day 361.
	Tertiary
CC1	
To evaluate the cell-mediated immune response induced in all study groups.	
 Frequency of HBsAg-specific CD4+/CD8+ T-cells per 10^6 CD4+/CD8+ T-cells producing at least 2 activation markers including at least 1 cytokine among IFN-γ, IL-2, TNF-α, IL-13, IL-17, 4-1BB and/or CD40L at Day 1, Day 8, Day 31, Day 38, Day 61 and Day 361. Frequency of plasmablasts, T Follicular Helper cells (TFH) and memory B-cells (flow cytometry) at Day 1, Day 8, Day 31, Day 38 and Day 61, in a subset of participants.
CC1	
	
 Frequency of HBsAg-specific memory B-cells (ELISPOT) at Day 1, Day 31, Day 61 and Day 361.
CC1	

AE = adverse event; **SAE** = serious adverse event; **MAE** = medically attended event; **pIMD** = potential immune-mediated disorder; **GMC** = geometric mean concentration; **HBs** = Hepatitis B surface antigen; **Ab** = antibody; **CC1** [REDACTED]

[figure not shown]
CC1 [REDACTED]

CC1 [REDACTED]

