2080	Participants did not comply with vaccination schedule: 
 
Number of days between Visit 1 and Visit 4 is outside [21-42 days] for all study groups
 
Number of days between Visit 4 and Visit 8 is outside [136-164 days], for HBs-alum group
 
	From the specific visit the condition is met.	PPS
2090	Participants did not comply with blood sample schedule (any of the below options): 
 
Number of days between Visit 1 and Visit 4 is outside [21-42] days
 
Number of days between Visit 4 and Visit 7 is outside [21-42 days]
 
Number of days between Visit 7 and Visit 9 is outside [286-314 days]
 
	At the specific visit (4 or 7 or 9) the condition is met	PPS
2100	Serological antibody results not available.	At the specific visit (1 or 4 or 7 or 9) the condition is met	PPS

Code	Condition under which the code is used	Visit when it is applicable	Applicable for analysis set/endpoint
2110	Blood sample for serological antibodies available but not yet tested (main analysis)	At the specific visit (1, or 4, or 7, or 9) the condition is met	PPS
2120	Issues in the lab results that are not related to handling of lab samples (Eg: Hemolysis, calibration of instruments) Unreliable released data as a result of confirmed sample mismatch or confirmed inappropriate sample handling at lab	At the specific visit the condition is met	PPS

CCI

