- The number and percentage of participants reporting each individual unsolicited AE category during the 31-day follow up period post-vaccination (i.e., the day of vaccination and 30 subsequent days) will be tabulated with exact 95% CI by event category (e.g., all, grade 3, related, grade 3 related, serious adverse events [SAEs], fatal etc.) for each group, after each dose and overall. Percentages will be computed based on the total number of exposed participants. Participants not reporting an AE will be considered as not having experienced any AE.
- The number and percentage of participants with any unsolicited AEs during the 31-day follow-up period (i.e. the day of vaccination and 30 subsequent days) will be tabulated with exact 95% CI by study group and categorized by Medical Dictionary for Regulatory Activities (MedDRA) system organ class (SOC) and preferred term (PT) (i.e. the table will be grouped by SOC and then preferred terms will be included within each group). Similar tabulation will be done for Grade 3 unsolicited AEs, for any causally related unsolicited AEs, for Grade 3 causally related unsolicited AEs and for unsolicited AEs resulting in a medically attended visit and at least one solicited or unsolicited adverse event excluding SAE. The verbatim reports of unsolicited AEs will be reviewed by a physician and the signs and symptoms will be coded according to the MedDRA Dictionary for Adverse Reaction Terminology. Every verbatim term will be matched with the appropriate preferred term. This will be done by group, after each dose and overall. The summary tables without SOC and PT information will be also produced for the follow-up period lasting until study end.
- The number and percentage of participants reporting each individual unsolicited AE during the 31-day follow-up period (i.e. the day of vaccination and 30 subsequent days) will be tabulated and ranked by MedDRA PT with the most common appearing first. This analysis will be done for each group after each dose and overall.
- The number and percentage of participants with at least one solicited or unsolicited medically attended event (MAE) reported any time between the day of vaccination (Day 1) and the end of the study period post vaccination (up to Day 61 for main analysis, up to Day 361 for final analysis) will be classified by MedDRA SOC and PT and tabulated with exact 95% CI. This analysis will be done by group.

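### The 31-day unsolicited-AE window after Dose 2 is closed by Visit 7 only if that visit is at least 30 days after Visit 4, but visits from 21 days are allowed and a participant with no report is counted as AE-free

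*Protocol*

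**What the plan says.** - **Endpoint.** Protocol Section 3 (Table 3) lists as primary: "Percentage of participants with any unsolicited AEs within 31 days (Day 1 till Day 31) after Dose 1 and Dose 2". SAP Section 4.2.1 tabulates these events "during the 31-day follow up period post-vaccination (i.e., the day of vaccination and 30 subsequent days". Protocol Section 10.3.8.1 sets the collection rule, with no exception for visit timing: "All other AEs occurring within 31 days following Dose 1 and Dose 2 of study intervention administration should be recorded".
- **Closing visit.** Protocol Table 2 gives 30 days as the optimal interval from Visit 4 to Visit 7 and allows 21 to 42. Footnote 1 asks for the optimal interval where possible. Footnote 2 ties the allowed range to eligibility for the immunogenicity Per-Protocol Set. SAP Table 4 uses the same range in code 2090, which applies when "Number of days between Visit 4 and Visit 7 is outside [21-42 days".
- **Contacts afterwards.** The last phone contact (PC10) is at Day 45, before Visit 7. After Visit 7, four groups are next scheduled at Visit 9, 286 to 314 days later. HBs-alum has Visit 8, 136 to 164 days after Visit 4.
- **Capture route.** Under Protocol Section 10.3.4, participants contact the site about medically attended events and anything that concerns them. All other unsolicited AEs "will be collected during an interview with the participants and by review of available medical records at the next visit". SAEs, MAEs and pIMDs are collected to study end (Section 10.3.8.1).
- **Analysis.** SAP Section 4.2.1 uses all exposed participants as the denominator and adds: "Participants not reporting an AE will be considered as not having experienced any AE".

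**The concern.** The length of the safety window and the tolerance on the visit that closes it were set separately. The tolerance serves the immunogenicity analysis, and nothing requires Visit 7 to reach the last day of the safety window. A site that sees a participant at 21 days is fully compliant, yet part of the primary window is still to come.

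The events at risk are non-serious ones that need no medical attention and do not worry the participant. They include symptoms on the solicited list that start after the 14-day diary period, because Section 10.3.4 makes these unsolicited AEs. A mild headache on post-Dose-2 Day 25 belongs in the endpoint, is unlikely to prompt a call, and is easily forgotten months later.

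The error can only lower the percentage, for an antigen-adjuvant combination that Protocol Section 2.3.3 says had not been tested in humans. The tables would not reveal it. For solicited events the SAP drops participants without a completed diary from the denominator (Section 1.1) and tabulates diary completion (Section 6.2). For unsolicited AEs it describes no counterpart.

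**Working it through.** **1. The plan's own calendar.** At optimal intervals, Visit 4 is Day 1 + 30 = Day 31. The window is Day 31 plus 30 days = Day 61. Visit 7 is Day 31 + 30 = Day 61. Window and visit end together, as Protocol Table 11 shows (D31 to D61).

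**2. Early Visit 7.** Dosing day is post-dose Day 1, so a visit k days later is post-dose Day k + 1. Full window days left = 31 - (k + 1).

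| Visit 4 to Visit 7 (days) | Post-dose day | Days left | Share of 31 |
|---|---|---|---|
| 21 | 22 | 9 | 29.0% |
| 23 | 24 | 7 | 22.6% |
| 25 | 26 | 5 | 16.1% |
| 27 | 28 | 3 | 9.7% |
| 29 | 30 | 1 | 3.2% |
| 30 or more | 31 or later | 0 | 0% |

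**3. Wait to the next scheduled contact.**
- HBs-AS03, HBs-AS04, HBs-AS37_50, HBs-AS37_100: 286 to 314 days after Visit 7 (Table 2).
- HBs-alum, Visit 7 at 21 days: 136 - 21 = 115 to 164 - 21 = 143 days. At optimal intervals it is 150 - 30 = 120 days.

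The Dose 1 window has no such gap, because Visit 5 and PC6 to PC10 follow Visit 4.

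**4. Extreme bound on the bias.** Assume a constant hazard over the 31 days, every participant seen at 21 days, and no later event captured. With true proportion p, the observed proportion is 1 - (1 - p)^(22/31).

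| True p | Observed |
|---|---|
| 10% | 7.2% |
| 20% | 14.6% |
| 30% | 22.4% |
| 40% | 30.4% |

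**5. Partial early attendance.** If a share s attends at 21 days and the rest at 30 days or later, the observed proportion is (1 - s) × p + s × (value from step 4). For p = 30%:
- s = 10%: 0.9 × 30 + 0.1 × 22.4 = 29.2%
- s = 25%: 0.75 × 30 + 0.25 × 22.4 = 28.1%
- s = 50%: 0.5 × 30 + 0.5 × 22.4 = 26.2%

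Neither p nor s is given in the documents; both are assumed.

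**The case against.** The strongest defence is that the schedule works as designed. The optimal visit falls on the last day of the window, Table 2 asks sites to aim for it, and 21 to 42 days is only a tolerance. This stands: only visits at 21 to 29 days are affected.

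A second defence is that other routes remain open. Medically attended events and events of concern are self-reported, the next-visit interview is paired with a review of medical records, and SAEs, MAEs and pIMDs are collected throughout. This also stands, and it makes the step 4 figures a bound. If half of the late events were still captured (assumed) and 25% attended at 21 days, a true 30% gives 0.75 × 30 + 0.25 × [1 - 0.7^(26.5/31)] × 100 = about 29.1%. Exact 95% intervals near 30% run from 13% to 53% for 7/23 and from 15% to 49% for 9/30, so such shifts lie well inside the sampling error. Sampling error is displayed, however, while a one-directional loss of follow-up is not.

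A reader might infer three stronger things that the documents do not support:
- *That every day after Visit 7 is unobserved and scored as event-free.* The SAP rule works per participant. Anyone with an AE already recorded in the window is counted correctly, and the routes above stay open.
- *That the comparison with alum is materially biased.* The recall delay does differ (about 4 months in HBs-alum, about 10 months elsewhere). But the safety analyses are descriptive and by group, no figure shows that recall differs materially, and no scheduled Visit 8 or 9 contact precedes the Day 61 cut-off. Any difference could enter only the final analysis.
- *That an extra phone call would still repair this trial.* The rationale for Amendment 4 cites main-analysis results collected from all participants after Dose 2 (Day 61), so every Dose 2 window had closed.

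**Conclusion.** The point holds for early attenders and for minor AEs. The plan allows a compliant Visit 7 that leaves up to 9 of 31 days (29%) of a primary safety window without scheduled follow-up for months, and it counts participants without a report as AE-free. The post-Dose-2 percentage can therefore be biased downward, and no planned table shows by how much.

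For a true 30%, the effect runs from none (all at 30 days or later) to an observed 22.4% at the extreme bound, with 29.2% to 26.2% if 10% to 50% attend at 21 days. These figures rest on a constant hazard and on no late event being captured, so with any late capture the effect would be smaller. The actual mix of visit days is not in the documents. It will be in the trial data, and a cheap check can use it.

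**What to change.** In SAP Section 4.2.1:

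1. Report, per group, how many exposed participants who received Dose 2 had Visit 7, or another recorded contact at which AEs were asked about, on or after post-Dose-2 Day 31. Visits 8 and 9 should not count here, because they rely on recall months later.
2. Repeat the post-Dose-2 unsolicited-AE table restricted to these participants, as a sensitivity analysis beside the planned table.

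The dates needed are already collected. The cost is one or two extra tables and a smaller n in the restricted one. The restricted percentage is free of the early cut-off, but reading it as the group's percentage assumes that the timing of Visit 7 is unrelated to AE risk.

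A phone contact at day 30-31 after Dose 2 for early attenders would have closed the gap at source. It is now an option only for future studies with this schedule.
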